If one of the two active treatment regimens offers more promise than the other and if the percentage of responders is greater than the anticipated 20-30% responder rate typically seen with placebo, we would then choose that option for the next larger and definitive placebo-controlled study. The sample size in this study is likely too small to show statistically significant differences between the groups.

This initial duration-finding study focuses on patients with persistent symptoms despite having received the standard antibiotic therapy for Lyme disease. While it would be reasonable from a scientific perspective to examine whether this particular treatment would be effective at the time of early Lyme disease, it would be considered unethical without additional data to experiment on patients by randomizing them to something other than what is already known to be helpful for most patients with early Lyme disease (e.g., about 80% of patients respond well to doxycycline or amoxicillin treatment of the Lyme rash).

For our proposed initial study, therefore, our focus of attention will be on patients who have already tried the standard course of treatment but who relapsed or not responded adequately; these patients are urgently in need of a cure for their disabling relapsing symptoms. Currently there is no evidence-based treatment for these patients.

Specific Aims and Hypotheses

Specific Aims and Hypotheses

Specific Aims and Hypotheses Specific Aims and Hypotheses

There are two primary aims. First, we will assess the safety and side effect profile of disulfiram among patients with post-treatment Lyme symptoms. Second, we will investigate whether treatment with disulfiram results in a meaningful reduction in fatigue and improvement in the quality of life among patients with Post-treatment Lyme Disease. Fatigue will be assessed by the Fatigue Severity Scale (FSS) and quality of life will be assessed with the Quality of Life Enjoyment and Satisfaction Questionnaire (Q-LES-Q).

There are several secondary goals.

1. We will examine whether there is a difference in the proportion of responders on the fatigue scale among the 2 different dosing regimens (54 days over 8 weeks vs. 26 days over 4 weeks followed by placebo). We will assess both the percentage of responders and magnitude of the effect.

2. We will examine whether there is an improvement on the secondary outcome measures.

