For in-person participants who opt to complete paper versions of the questionnaires, this data will be stored in locked files and will be kept confidential to the extent permitted by law. Research binders will be available only to research staff and Federal, State and Institutional personnel as part of routine audits. Paper versions of self-report questionnaires will be labeled with a research number assigned to the patient, not the patient's name.

Wearing of activity monitor

All participants will be provided with an activity monitor (e.g., Fitbit) to keep track of sleep and of the number of steps taken each day. Participants will wear this device for 2 weeks prior to randomization and throughout the 14 weeks of the study. We will also inform the participants that they will need to share the data from their devices periodically during their study visits.

Phone-calls at end of Weeks 3, 5,7, 9 and 12 (10-20 mins)

The follow-up phone calls will be done by one of the study clinicians and will focus on inquiring about the following-

- If the participant is experiencing side-effects related to disulfiram
- If the participant is adhering to the study treatment
- If the participant has used any kind of substance like alcohol, cannabis etc.
- If the participant has started any new medications

Treatment Phase

Patients will be randomly assigned to one of two groups.

Both groups (the 4 week duration and the 8 week duration groups) will share the same protocol for the first 4 weeks as follows:

- Week 1 Disulfiram 250 every other day
- Week 2 Disulfiram 250 daily.
- Week 3 Disulfiram 250 alternating with 500
- Week 4 Disulfiram 500 daily.

Week 5-8 Continue with 500 daily (2 pills daily of disulfiram or placebo) or lower if needed based on side effects. (Note: the last 4 weeks of the study are double-blind)

(The long duration group will increase to two pills daily (500 mg) or the highest dosing regimen they can tolerate without significant side effects, while the short duration group during the last 4 weeks of the treatment period will be given placebo pills).

In-person patients will be seen in the clinic at least every 2 weeks to week 10 and at week -14 for a followup. Remote and Hybrid patients will be seen in via scheduled telehealth sessions at least every 2 weeks up to week 10 and at week -14 for follow-up. Additionally, when not seen in person or via telehealth, patients will be followed up weekly over the phone to week 12.

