Should a patient need to be discontinued from the study before week 10, he/she will be asked to return to NYSPI or to complete a telehealth evaluation and an assessment with their local physician (if participating remotely) to complete the major week 8/10 assessments so that his/her progress can continued to be evaluated by the study clinician. Since we do not know the optimal duration of disulfiram (ie, shorter courses may be effective) and because improvement may occur during the weeks after discontinuation, we will ask patients to return at week 10 (or to complete telehealth and local evaluations) but also to complete self-reports assessments and telephone follow-up at home at weeks 2, 6, 8, and 14.

Should a patient who drops from treatment early plan to start a new treatment that might impact clinical ratings, we will ask the patient to complete the full set of week 10 assessments early so that these can be used in the final data analysis; that patient will then be discontinued from both the treatment and assessment phase of the study. The patient will also be asked to return all study medication which we will then return to the NYSPI pharmacy.

During COVID-19 pandemic: I attest to follow the COVID-19 Safety Guidelines for Columbia Psychiatry and NYSPI Re-Entry outlined in the NYSPI Director's June 1st memo, which include but are not limited to:

• Infection Control/PPE – Guidelines

• Research participants will only come on-site if absolutely necessary for study procedures.

• No volunteers/externs on-site during Stage 1.

• Clinical research teams will screen their participants for COVID symptoms (night before and day of onsite visit, documenting this in the chart), and escort them in and out of the building.

• COVID/COVID-like symptoms in participants will be reported to the IRB via PRISM as an SAE.

You can upload charts or diagrams if any

Criteria for Early Discontinuation

Criteria for Early Discontinuation

Patients will be monitored for global clinical change (CGI Change - clinician rating) and for side-effects of the medications (Saftee) during the clinic visits or telehealth visits and weekly phone check-ups.

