1. SAFTEE

Please attach copies, unless standard instruments are used

Off label and investigational use of drugs/devices

Choose from the following that will be applicable to your study ✓ Drug Select the number of drugs used in this study 1

Drug #1

Name of the drug Disulfiram Manufacturer and other information

Disulfiram is FDA approved to help individuals wishing to abstain from alcohol. There are several manufacturers of disulfiram.

Approval Status IND is approved IND# 142979 Who holds the IND/IND sponsor? IND is held by PI/CU Investigator [name], MD

Research Related Delay to Treatment

Will research procedures result in a delay to treatment? Yes

Maximum duration of delay to any treatment

We are asking patients not to start any new treatments during the course of this study and for 3 months prior. Therefore, the delay in starting any new treatment will be approximately 6.5 months.

Treatment is provided to all the participants. However, the participants who are randomized to the shorter dose regimen will receive 26 days of treatment compared to the participants who will get treatment for 54 days.

Maximum duration of delay to standard care or treatment of known efficacy

There is no treatment of known efficacy for patients with post-treatment Lyme disease.

Treatment to be provided at the end of the study

Patients will be offered the option of 3 months of symptom-based clinical treatment at the end of the study. The clinician visits at PI will be free. Patients will be given scripts of medication if needed, the cost of which will be covered by them or their insurance carrier.

Clinical Treatment Alternatives

Clinical treatment alternatives

The treatment of post-treatment Lyme disease symptoms is a matter of considerable uncertainty. Some health care providers offer repeated courses of antibiotics while other health care providers offer symptom-based therapies. Unfortunately too few studies have been conducted among patients with post-treatment Lyme disease to recommend specific treatments.

Risks/Discomforts/Inconveniences

Risks that could be encountered during the study period

Treatment with Disulfiram

1. Disulfiram-alcohol reaction. If patients consume alcohol or alcohol-containing products while on disulfiram, the patient may experience diaphoresis, palpitations, facial flushing, nausea, vertigo, hypotension, and tachycardia.

2. Disulfiram-related adverse effects.

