Study Objectives	A study is a preliminary investigation regarding the relative benefit of 4 vs 8 weeks of treatment with disulfiram. With this initial study, the investigators will be able to evaluate the side effects, tolerability and initial signs of the effectiveness of disulfiram in reducing symptoms among the 24 patients assessed. The results of this study will guide the investigators regarding whether a larger definitive randomized trial should be conducted, and which treatment schedule is optimal.
Primary endpoint	Week 10 evaluation.
Study Design	A small 14-week randomized placebo-controlled pilot study enrolling 24 patients with persistent symptoms despite prior antibiotic treatment for Lyme disease (known as Post-treatment Lyme Disease Syndrome). Among the 24 disulfiram-treated patients, half will get 8 weeks of disulfiram and the other half will get a shorter duration of disulfiram for 4 weeks followed by 4 weeks of matching placebo. After week 8, patients will be off pills for 2 weeks for the primary week 10 evaluation and then for another 4 weeks for the week 14 follow-up evaluation. This will be a double-blinded study; neither physician nor patient will know which treatment group the patient is assigned to. For details see PSF.
General Study Population	See PSF respective section
Inclusion- Exclusion Criteria	See PSF respective section
Study Assessments	See PSF respective section
Sample size	24 as of 04/02/2019. The study was terminated in 2022 with a sample size of 11.
Randomization	This will be a double-blinded study; neither physician nor patient will know which treatment group the patient is assigned to. Randomization is performed at New York Psychiatric Institute pharmacy when medication is issued to an enrolled participant. Randomization is performed in blocked of 12. The study unblind will occur when the enrollment is completed, and all patients finish their follow-up assessments.
Primary aim#1	To assess the safety and side effect profile of disulfiram among patients with post treatment Lyme symptoms. This will be assessed by SAFTEE (systematically) as well as recording all unanticipated adverse events/serious adverse events.
Primary aim #2	To investigate whether treatment with disulfiram results in a meaningful reduction in fatigue and improvement in the quality of life among patients

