Analysis Analysis Population Missing Data Interim Analyses and Data	The rationale for the Fitbit is that our primary outcome is fatigue. People who are less fatigued may be engaging in more activity, such as doing more steps during the day. Moreover, activity monitoring using a device such as a Fitbit is being increasingly used in research studies as a measure of the change in response to treatment. Analysis will be performed after the study is unblinded. We conduct intent to treat analysis which covers all enrolled patients who received a study drug and who participated in at least one post-baseline assessment. Missing data is treated as missing at random

Primary aim#1 analysis	Tables on all mortality rate, SAE and AE will be generated. To estimate safety, number of adverse events in active and sham treatment groups by the end of 10-week period will be computed and reported.
Primary aim#2 analysis	To investigate whether treatment with disulfiram results in a meaningful reduction in fatigue and improvement in the quality of life, a change in scores between the baseline and week 10 will be computed. We will calculate a number of participants who's change in score reached a minimal clinically significant difference (MCID) for each of the measures. MCID for Fatigue Severity Scale (FSS) and MCID for Quality-of-Life Enjoyment and Satisfaction Questionnaire (Q-LES-Q) is 6.8. A Log Odds ratio for 8-week and 4-week group will be computed along with the 95% confidence interval for this ratio. The 95% confidence interval provides considerably more information than testing a specific null hypothesis: it provides a range of plausible values for differences in these primary outcomes between treatment groups which can be used to inform research in larger studies.

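### The primary safety analysis counts adverse events in 'active' and 'sham' groups, but both randomised arms take disulfiram and their assigned treatment differs only in weeks 5-8

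*Combined protocol and SAP*

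**What the plan says.** The SAP row 'Primary aim#1 analysis' promises tables of deaths, serious adverse events and adverse events, with no grouping or time period stated. Its only stated comparison is: "To estimate safety, number of adverse events in active and sham treatment groups by the end of 10-week period will be computed and reported".

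The rest of the plan defines the groups differently:

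- SAP, 'Study Design': one half stays on disulfiram throughout the 8 weeks; for the rest, "the other half will get a shorter duration of disulfiram for 4 weeks followed by 4 weeks of matching placebo".
- Protocol, 'Treatment Phase': there are two randomised groups, and they "will share the same protocol for the first 4 weeks as follows".
- Protocol, 'Research Related Delay to Treatment': "Treatment is provided to all the participants".
- Secondary goal 1 (protocol and SAP) gives the drug days: "54 days over 8 weeks vs. 26 days over 4 weeks followed by placebo".
- Protocol, 'Rationale': a larger efficacy comparison of disulfiram with placebo was deliberately not the first step.
- SAP, 'Primary aim#2 analysis', the next row, uses names that do match the arms: "A Log Odds ratio for 8-week and 4-week group will be computed".

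In the text available, the only other use of the word 'sham' is a generic tick-box in the procedures checklist. Secondary goal 3 covers side effects and drop-out by treatment schedule, but the available SAP has no analysis row for it.

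**The concern.** Safety is a primary aim, and tolerability helps decide whether a placebo-controlled trial follows. The progress report also gives adverse-event drop-out above expectation as one reason why enrolment stopped. The safety comparison is therefore one of the main things that readers will take from this trial.

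Groups called 'active' and 'sham' tell the reader that one was treated and the other was not. Similar counts would then suggest that disulfiram adds little harm. In this design, similar counts could equally mean that the harm arose in the first four weeks, while the dose was being raised and both arms were on drug.

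**Working it through.** **1. Assigned treatment over the 10 weeks counted** (SAP 'Study Design'; protocol 'Treatment Phase')

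| Weeks | 8-week arm | 4-week arm | Same? |
|---|---|---|---|
| 1-4 | disulfiram, shared schedule | disulfiram, shared schedule | yes |
| 5-8 | disulfiram | placebo | no |
| 9-10 | no pills | no pills | yes |

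The arms are assigned the same treatment in 4 + 2 = 6 of 10 weeks. Weeks on drug are 8 and 4. On the stated days, 54 - 26 = 28 days = 4 weeks, so the whole difference lies in weeks 5-8. The 4-week arm still has 26/54 = 48% of the other arm's stated drug days. Neither arm can be called sham over the period counted.

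**2. What the between-arm difference contains.** Per participant, let *b* be the expected background events to week 10, *x1* the drug-related excess in weeks 1-4, and *x2* the excess in weeks 5-8 on drug. Assume full adherence and no carry-over.

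- 8-week arm: *b + x1 + x2*
- 4-week arm: *b + x1*
- Difference: *x2*
- Difference from an untreated group, which the trial does not have: *x1 + x2*

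The difference shows the share *x2/(x1 + x2)* of the 8-week arm's excess. That is 0 if all excess falls in weeks 1-4, 1/2 if *x1 = x2*, and 1 if all falls in weeks 5-8. The documents give neither *x1* nor *x2*, so no single figure follows. The share is a property of any 4- versus 8-week contrast and is the same whatever the groups are called. What the label changes is the meaning given to the numbers: *x1* in the 4-week arm is reported as events under sham.

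**3. Can events be placed in time?** Visits fall in weeks 1, 2, 4, 6, 8 and 10, and calls in weeks 3, 5, 7 and 9. A participant who stays in the study thus has a contact in every week from 1 to 10. Participants are monitored "for side-effects of the medications (Saftee) during the clinic visits or telehealth visits and weekly phone check-ups". There are three limits.

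- For participants who discontinue before week 10, the protocol asks for self-reports and telephone follow-up at weeks 2, 6, 8 and 14, plus a week 10 assessment. Those starting a new treatment do the week 10 assessments early and then leave. Weekly contact is not stated for either group.
- Remote and hybrid participants have safety laboratory tests at weeks 6 and 10 but not at week 8. A finding first seen at week 10 could have arisen on or off pills.
- The calls ask about side effects related to disulfiram, so they may miss events not attributed to it.

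**4. Precision.** Eleven participants were enrolled. The split by arm is not given; assume 5 in one arm. If 2 of 5 have an event, the exact (Clopper-Pearson) 95% interval is 5% to 85%.

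**The case against.** The strongest reply is that this is a slip of wording. There are only two groups, the same SAP table defines them, and the next row names them properly. 'Sham' can then hardly mean anything but the arm that takes matching placebo in weeks 5-8. Relabelling changes no number, and the count by randomised arm is a valid comparison of 4 with 8 weeks. All of that stands, and the count should be kept. But the wrong label sits in the only row that specifies the primary safety analysis, and it changes what the reported numbers are taken to mean.

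A second reply is that the promised adverse event tables may be split by period anyway. The plan is silent on their layout. One may say that a split is not specified, but not that the plan rules it out.

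A reader might also infer two stronger things that the documents do not support. One is that the analysis is invalid or hides a known part of the drug's harm, for instance half. That share needs event rates by period, which the documents do not give; step 2 allows anything from none to all. The other is that the trial has no placebo comparison at all. Weeks 5-8 provide one, randomised and double-blind.

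**Conclusion.** The concern holds as an error in how the primary safety analysis is specified. The groups named do not exist. If 'sham' is read as the 4-week arm, that arm's on-drug events would be reported as sham events, and a duration contrast would be presented as drug versus no drug. This follows from the text alone. That the between-arm difference omits any excess from weeks 1-4 follows from the shared schedule. How large that excess is, and so how misleading the label would be, cannot be derived from the documents.

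The error should be fixed because it affects a primary aim and is cheap to correct. It does not invalidate the count by arm.

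One mismatch seen in passing is a separate point. The schedule begins "Week 1 Disulfiram 250 every other day", which gives 3 or 4 dosing days in week 1. With 21 days in weeks 2-4 this makes 24 or 25, and with 28 more it makes 52 or 53, against the stated 26 and 54. Those sections must be reconciled, but nothing above depends on which count is used.

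**What to change.** In the 'Primary aim#1 analysis' row, replace 'active and sham' with '8-week and 4-week', and keep the cumulative count by randomised arm to week 10.

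Add one descriptive table giving events, participants with at least one event, and person-days at risk. Person-days are needed because the periods differ in length. Use mutually exclusive periods:

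1. Weeks 1-4 while taking disulfiram, arms pooled.
2. Weeks 5-8 while taking assigned pills, by arm (disulfiram versus placebo), with the number in each arm still on pills at week 5.
3. After the last study pill, by arm: early stoppers from their stop date, all others from week 9.
4. Period uncertain: events that cannot be placed. This includes laboratory findings first seen at week 10 in remote and hybrid participants, and events in discontinued participants whose contacts do not settle the timing.

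Use the onset date if it was recorded (the available text does not say), otherwise the contact at which the event was first reported. Take stop dates from the pill logs. Make no formal inference, and mark the table post hoc if unblinding has occurred.

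The cost is one wording change and one table from contacts and logs already planned. The table has limits that should be stated with it:

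- Counts will be very small.
- Drop-out before week 5 shrinks the only disulfiram-placebo period, and stopping during weeks 5-8 may itself depend on arm.
- Weeks 1-4 have no untreated comparison.
- Drug effects may carry over into the placebo weeks. The protocol requires alcohol avoidance for 6 weeks after the last dose, so it does not treat the effect as ending with the last pill.

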Have all study staff with a significant role in the design or implementation of the human subject components of this study received required training in human research subject protections? Yes

Is the study covered by a certificate of confidentiality? No

Overall Progress

Approved sample size

24

Total number of participants enrolled to date

11

Number of participants who have completed the study to date

10

Have there been any significant deviations from the anticipated study recruitment, retention or completion estimates?

Yes

Describe actions taken or planned to address these problems.

The study enrollment was stopped in 2021 for the following reasons: a) the treatment drop-out rate in our study due to adverse events has been higher than expected; b) funding for this project is nearly complete; c) our pilot study has provided useful information about the relative safety of lower doses of disulfiram and the possibility of benefit with treatment; and d) based on the literature, disulfiram is a drug with uncommon but serious risk of toxicity.

Comments / additional information

Sample Demographics

Select the # of samples applicable

Specify population

Patients with Post-Treatment Lyme Disease Syndrome

Total number of participants enrolled from this population to date

11

Gender, Racial and Ethnic Breakdown

Sex: Female (6, 54.0%) Male (5, 46.0%) Racial Background: American Indian or Alaska Native (0, 0.0%) Asian (0, 0.0%) Native Hawaiian or Other Pacific Islander (0, 0.0%) Black or African American (1, 9.0%) White (10, 91.0%) More Than One Race (0, 0.0%) Other: (0, 0.0%) Ethnic Background: Hispanic or Latino (2, 18.0%) Not Hispanic or Latino (9, 82.0%)

Summary of Current Year's Enrollment and Drop-out

Number of participants who signed consent in the past year 0 Number of participants currently enrolled 0 Did the investigator withdraw participants from the study? No Did participants decide to discontinue study involvement? No

New York State Psychiatric Institute INSTITUTIONAL REVIEW BOARD

Procedures

To create the protocol summary form, first indicate if this research will include any of the following procedures

- Collection of Biological Specimens
- ✓ Internet-based Data Collection or Transmission
- ✓ Medication Trial
- ✓ Medication-Free Period or Treatment Washout
- ✓ Neuropsychological Evaluation
- ✓ Off-label Use of Drug or Device
- ✓ Psychiatric Assessment
- ✓ Use of Placebo or Sham Treatment

Population

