Our initial pilot study will focus on patients with persistent symptoms despite having received the standard antibiotic therapy (or more) for Lyme disease. Because no one has yet studied the safety of disulfiram for

patients with a history of Lyme disease and because we do not know the optimal treatment duration for disulfiram, our initial effort will have the primary aims of assessing safety and determining whether a longer course of daily treatment is more effective than a shorter course of daily treatment.

We propose therefore a small 14-week randomized placebo-controlled pilot study enrolling 24 patients with persistent symptoms despite prior antibiotic treatment for Lyme disease (known as Post-treatment Lyme Disease Syndrome or "chronic Lyme"). Among the 24 disulfiram-treated patients, half will get 54 days of disulfiram treatment over the course of 8 weeks and the other half will get a shorter duration of disulfiram for 26 days given over the course of 4 weeks. After week 8, patients will be off pills for 2 weeks for the primary week 10 evaluation and then for another 4 weeks for the week 14 follow-up evaluation. This will be a double-blinded study; neither clinician nor patient will know which treatment group the patient is assigned to.

With this initial study, we will be able to evaluate the side effects, tolerability and initial signs of effectiveness of disulfiram in reducing symptoms among the 24 patients assessed. The results of this study will guide us regarding the safety of disulfiram among patients with Lyme disease and whether a definitive randomized trial should be conducted; it will also inform us regarding which treatment schedule is optimal.

Background, Significance and Rationale

Background, Significance and Rationale

About 10-20% of patients treated with standard antibiotic therapy suffer from persistent relapsing-remitting symptoms. Persistent infection may account for the persistent symptoms in some of these patients, as persistent infection after antibiotic treatment has been well-documented in several animal models of Lyme disease. Clearly, a more effective antibiotic is needed

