All the shared samples will be assigned a unique subject ID and no PHI will be shared with the collaborators. Samples will be shared after obtaining a Material Transfer Agreement (MTA).

Will the study be conducted under a certificate of confidentiality? No

Direct Benefits to Subjects

Direct Benefits to Subjects

There is no direct benefit to the participants expected from participation in this research study. It is hoped,

however, that the knowledge gained from this study may lead to a significant public health benefit as we hope it will help establish the safety and suggest efficacy of disulfiram as a medication to treat chronic symptoms of Lyme disease. While we hypothesize that patients will experience a reduction in symptom burden as a result of participation in this study, we are not certain this will be the case. Therefore, at this point, we cannot state that there will be direct benefits to the subjects.

Compensation and/or Reimbursement

Will compensation or reimbursement for expenses be offered to subjects?

Yes

Please describe and indicate total amount and schedule of payment(s).

Include justification for compensation amounts and indicate if there are bonus payments.

Participants who live outside the NYC metro area and choose to participate in-person will be reimbursed for reasonable travel expenses up to \$100 per visit. The amount is considered proportionate to the costs of rail travel for participants that live along the Northeast corridor and/or cover costs incurred for paid parking. For participants traveling from interstate, the reimbursement may be used to subsidize the cost of accommodation for each visit. Remote participants will not receive reimbursement. During the COVID-19 Pandemic, we will reimburse travel for participants within and outside the NYC metro area so that it may be more feasible for them to avoid public transportation. Hybrid participants will be reimbursed for reasonable travel expenses up to \$200 per visit.

References

References

Long TE. Repurposing thiram and disulfiram as antibacterial agents for multi-drug resistant Staphylococcus aureus infections. Antimicrobial agents and chemotherapy. 2017 Jul 3:AAC-00898.

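### The first primary aim, safety, is summarised by raw adverse event counts, with no proportion of participants affected and no interval

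*Combined protocol and SAP*

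**What the plan says.** The SAP names safety as primary aim #1, to be assessed by SAFTEE and by recording unanticipated adverse and serious adverse events. The Primary aim#1 analysis row has two sentences: "Tables on all mortality rate, SAE and AE will be generated", and one that begins "To estimate safety, number of adverse events" and takes that count by active and sham group up to week 10. For safety it specifies no denominator, no proportion of participants with an event and no confidence interval.

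The next row, for primary aim #2, plans a 95% confidence interval for the log odds ratio and explains that an interval is more informative than a test because it shows the range of plausible values for use in larger studies.

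Under Treatment Phase, both arms follow the same disulfiram schedule in weeks 1-4. Only in weeks 5-8 does the short-duration arm take placebo. The Sample size row reads "24 as of 04/02/2019. The study was terminated in 2022 with a sample size of 11".

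The Significance section makes good tolerability, together with a suggestion of efficacy, the condition for a subsequent placebo-controlled trial. The Rationale gives a numerical rule for a negative efficacy finding (30% or fewer responders). Tolerability has none.

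**The concern.** A raw event count has three weaknesses here.

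First, it mixes frequency with clustering. As an illustration, six events among 11 people could come from one participant (1/11 = 9%) or from six (6/11 = 55%).

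Second, the active and sham labels do not fit the design. Both arms are on disulfiram for the first four weeks, so a count up to week 10 would place on-drug events of the short-duration arm under the sham heading.

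Third, a count without an interval does not say what rate of harm is still possible. For serious events the count is likely to be small or zero, and the sample is small enough that the remaining uncertainty is wide.

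What is at stake is the value of the pilot's safety result for its stated use: "The results of this study will guide us regarding the safety of disulfiram among patients with Lyme disease". A reader deciding whether the tolerability condition is met would have a number of events but no proportion and no precision.

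**Working it through.** The documents state no safety precision, detectable rate or confidence level for safety, so there is no planned figure to reproduce. The check asks what the planned output would leave open.

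**Inputs**
- n = 24: planned sample, all to receive disulfiram (SAP, Study Design and Sample size rows).
- n = 12: one planned arm (half of 24).
- n = 11: sample at termination (SAP, Sample size row). The split of the 11 between arms is not stated.
- Confidence level: the SAP uses 95% for efficacy. Two-sided 95% is taken as the main case and one-sided 95% shown beside it. Both are assumptions for safety.

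**Upper limit with zero events**

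Exact (Clopper-Pearson) limit: two-sided 95% is 1 − 0.025^(1/n); one-sided 95% is 1 − 0.05^(1/n).

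| n | two-sided 95% | one-sided 95% |
|---|---|---|
| 24 | 14.2% | 11.7% |
| 12 | 26.5% | 22.1% |
| 11 | 28.5% | 23.8% |

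**If fewer than 11 were dosed**

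The number dosed is not stated exactly: 11 were enrolled, 10 completed, and two of six who consented in 2021 were ineligible. At n = 10 the limits are 30.8% and 25.9%; at n = 9 they are 33.6% and 28.3%.

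**Chance of seeing no case at an assumed true incidence p**

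Formula: (1 − p)^n.

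| p (assumed) | n = 24 | n = 12 | n = 11 |
|---|---|---|---|
| 10% | 8% | 28% | 31% |
| 5% | 29% | 54% | 57% |

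**Non-zero counts**

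The interval is just as useful here. Two participants affected out of 11 (illustrative) gives 2/11 = 18%, with an exact two-sided 95% interval of 2.3% to 51.8%.

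**What an interval cannot do**

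The risk section cites neuropathy at 1 per 10,000 patients per year. Used unadjusted as a per-person risk, the chance of at least one case is 1 − (1 − 0.0001)^n, which is 0.24% for 24 people and 0.11% for 11. No analysis of this sample can speak to harms that rare. The interval's use is for tolerability and commoner harms.

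**The case against.** The strongest reply is that this is a descriptive pilot and the documents are candid about harm. The same sentence that says "our pilot study has provided useful information about the relative safety of lower doses of disulfiram" also reports more adverse-event drop-out than expected and refers to uncommon but serious toxicity. The progress report notes the small sample, and the Rationale says that significant differences between groups are unlikely. SAFTEE collects events systematically, secondary aim 3 covers side effects and drop-out by schedule, and anyone given 0/11 can compute the limit. Tolerability depends mainly on common side effects and drop-out, not on excluding rare events.

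Much of this stands, and it limits the point. Four stronger readings are tempting and should not be made:

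- A reader might infer that the plan equates few or no serious events with safety. No text says so. The statement "we hope it will help establish the safety and suggest efficacy of disulfiram" is an aspiration, in a section that promises no direct benefit.
- A reader might infer that risks of exactly 12% and 24% cannot be excluded by zero events in 24 and 11. At one-sided 95% they just are: 0.88^24 = 4.7% and 0.76^11 = 4.9%. The confidence level has to be stated with the limit.
- A reader might infer that the trial plans a confounded comparison of doses. The remark on lower doses is a reason given for stopping enrolment; the SAP plans no analysis by dose.
- A reader might fault the power of a between-arm safety test, or the lack of a margin. No such test is planned, and a descriptive pilot does not need a margin.

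What remains is that acknowledging a small sample does not quantify it, and the SAP gives its own reason for intervals but applies it only to the second primary aim.

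**Conclusion.** The omission is real and minor. As written, the row reports events rather than participants affected, uses group labels that do not match exposure in weeks 1-4, and gives no measure of uncertainty for a result on which a further trial partly depends. With zero events, rates up to 14.2% (24 participants), 26.5% (12) or 28.5% (11) would remain inside an exact two-sided 95% interval. These figures assume that all 24, 12 or 11 were dosed and followed, and they apply to one event type at a time. The wording of the documents does not support a claim that safety has been, or will be, wrongly concluded.

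**What to change.** In the Primary aim#1 analysis row, keep the tables and add the following.

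- For SAEs, adverse events leading to discontinuation, the liver stopping criterion being met, and new neuropathy or psychiatric events, report the number and proportion of dosed participants affected, with exact (Clopper-Pearson) 95% intervals.
- Pool all dosed participants for weeks 1-4, when both arms take disulfiram. From week 5 on, report by randomised arm and drop the sham label. State the denominator for each period.
- Use everyone who took a dose as the safety denominator. The SAP's analysis population also requires a post-baseline assessment, which could remove an early withdrawal.
- Where no event occurs, state the upper limit and its confidence level. Note that each interval is at 95% separately, not jointly.

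The cost is a few lines of text and one extra table column, from data already planned for collection. If the data have already been unblinded, mark the intervals as added afterwards. The downside is a safety statement that looks less favourable than a bare count.
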